3.1.2. Patient Well-Being

- Overall survival (OS) defined as the interval from start of study therapy to death from any cause
- Change from baseline in HRQL domain and symptom scores based on the Functional Assessment of Cancer Therapy: Leukemia (FACT-Leu) (see Appendix 2)
- Changes from baseline in Karnofsky performance status defined as the change from baseline in the performance status (see Appendix 3)

CONFIDENTIAL Page 38 21 September 2017

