9.3. Analysis Conventions

9.3.1. Analysis Sets

9.3.1.1. Intent-to-Treat Analysis Set

The ITT analysis set includes all subjects who receive ≥1 dose of any study treatment (high-dose idelalisib or standard-dose idelalisib). In the ITT analysis set, study drug assignment will be designated according to planned allocation in this study, regardless of whether subjects receive a different study therapy from that to which they were allocated.

This analysis set will be used in the analyses of subject characteristics and all the tumor control and patient well-being endpoints. Subjects in the ITT analysis set who do not have sufficient baseline or on-study tumor status information to be adequately assessed for response status will be included in the denominators in the calculation of response rates.

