9.3.2.2. Double-Blinded Portion of the Study Analyses

Efficacy and safety data collected during the blinded portion of Study GS-US-312-0117 will be presented in the following 2 groups:

- IDELA 300 mg BID: Subjects who have PD per IRC confirmation in Arm A of Study GS-US-312-0116 and subsequently enroll into Study GS-US-312-0117 to receive IDELA 300 mg BID during the double-blind portion of the study
- Placebo in Study GS-US-312-0116 + IDELA 150 mg BID in Study GS-US-312-0117: Subjects who have PD per IRC confirmation in Arm B of Study GS-US-312-0116 and subsequently enroll Study GS-US-312-0117 to receive IDELA 150 mg BID during the double-blind portion of the study

All analyses will be performed based on the data collected during the blinded-portion of the extension study. Time-to-event analyses will reference to the date of first treatment on this clinical trial (Study GS-US-312-0117). Similarly, evaluations of on-therapy changes will reference the baseline values obtained prior to treatment in this study. The baseline value used in each analysis will be the last (most recent) pre-treatment value. Analyses will be descriptive in nature and formal comparisons of outcomes in the 2 groups are not planned.

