9.4.2. Efficacy Analyses

9.4.2.1. Time-to-Event Tumor Control and Survival Endpoints

PFS, DOR and OS will be described in the ITT analysis set using Kaplan-Meier methods by treatment group. Medians, ranges, and corresponding 95% CIs will be presented.

The Cox regression approach may be used to explore the influence of the primary study stratification factors and other baseline characteristics on PFS and OS. The stratification variables from the primary study and additional baseline subject characteristics may be included as covariates, focusing on those with expected prognostic significance.

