3. GENERAL CONSIDERATIONS FOR DATA ANALYSES

3.1. Analysis Sets

3.1.1. Intent-to-Treat Analysis Set

The intent-to-treat (ITT) analysis set includes all subjects who are randomized in Study GS-US-312-0116 regardless of whether subjects receive any study drug(s), or receive a different regimen from the regimen they were randomized to. Treatment assignment will be designated according to randomization. This analysis set will be used for OS analyses.

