- Platelet response rate defined as the proportion of subjects with baseline thrombocytopenia (platelet count $< 100 \times 10^9/L$) who achieve an on-study platelet count $\ge 100 \times 10^9/L$ or demonstrate a $\ge 50\%$ increase in platelet count from baseline without need for exogenous growth factors. Platelet values within 4 weeks post-baseline or after 8 days post transfusion will be excluded from the platelet response rate evaluation.
- Hemoglobin response rate defined as the proportion of subjects with baseline anemia (hemoglobin < 110 g/L [11.0 g/dL]) who achieve an on-study hemoglobin ≥110 g/L (11.0 g/dL) or demonstrate a ≥ 50% increase in hemoglobin from baseline without red blood cell transfusions or need for exogenous growth factors. Hemoglobin values within 4 weeks post-baseline or after 4 weeks of receiving packed cell/whole blood transfusion or after 6 weeks receiving exogenous growth factors (e.g., Darbepoetin alfa) will be excluded for the hemoglobin response evaluation.
- Neutrophil response rate defined as the proportion of subjects with baseline neutropenia (absolute neutrophil count [ANC] ≤ 1.5 × 10⁹/L) who achieve an ANC > 1.5 × 10⁹/L or demonstrate a ≥ 50% increase in ANC from baseline without need for exogenous growth factors. ANC values within 4 weeks of post-baseline or after 2 weeks of receiving exogenous growth factors (e.g., Filgrastim, G-CSF, Lenograstim) or after 4 weeks of receiving Neulasta will be excluded for the neutrophil response evaluation.
- Overall Survival (OS) defined as the interval from the date of randomization in Study GS-US-312-0116 to death from any cause during the study or long term follow up
- Change from baseline in HRQL using FACT-Leu scores
- Changes from baseline in Karnofsky performance status
- Change from baseline in overall health and summary of single-item dimension scores as assessed using the EuroQoL Five-Dimension (EQ-5D) utility measure

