6.1.3. Between-Study Comparisons

6.2. Changes From Protocol-Specified Efficacy Analyses

The per-protocol analysis set and the safety analysis set are no longer applicable. The FAS will be used for both efficacy and safety analyses.

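### The open-label SAP counts OS from 0116 randomization in everyone randomized there, not from start of study therapy in dosed subjects as the protocol defines it, and SAP 6.2 does not list the change

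*SAP*

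**What the plan says.** **Protocol.** Section 3.1.2 and the synopsis agree on the endpoint: "Overall survival (OS) defined as the interval from start of study therapy to death from any cause". Section 9.3.1.1 sets the population: "The ITT analysis set includes all subjects who receive ≥1 dose of any study treatment", where the treatments named are the two idelalisib doses of this study. Section 9.4.2.1 joins the two: "PFS, DOR and OS will be described in the ITT analysis set using Kaplan-Meier methods by treatment group".

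**SAP.** Section 6.1.1 has "Overall Survival (OS) defined as the interval from the date of randomization in Study GS-US-312-0116 to death from any cause". Section 3.1.1 redefines ITT as all subjects randomized in 0116, dosed or not, and reserves that set for OS. Section 6.1.2.8 groups subjects by original 0116 arm. It adds two analyses: one censors Arm B at the first idelalisib dose, and the other is a rank-preserving structural failure time (RPSFT) model. Table 3-1 has a separate OS column with the 0116 randomization date. For the two Arm B groups, every other efficacy endpoint starts at first idelalisib.

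**Declared changes.** On efficacy, SAP 6.2 says "The per-protocol analysis set and the safety analysis set are no longer applicable" and that the FAS serves both efficacy and safety. It mentions neither the OS origin nor the new meaning of ITT.

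**The concern.** Two attributes of a protocol-defined endpoint have moved under unchanged labels, and the section meant to record such changes is silent. SAP 7.6 does record a smaller change, the dropped compliance summary, so a reader would expect this one to be listed too.

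The consequence falls on Arm B. Its OS curve under the SAP includes the placebo-plus-rituximab period and also subjects who never took idelalisib, whom SAP 3.5.1 excludes from the analyses by default. That curve answers the randomized 0116 question. It does not describe survival from the start of single-agent idelalisib, which is what the protocol endpoint measures. In the same report, Arm B PFS and OS would run on different clocks and in different sets of subjects.

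**Working it through.** **1. The definitions side by side**

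| | Protocol | Open-label SAP |
|---|---|---|
| Time origin | Start of study therapy (3.1.2) | 0116 randomization (6.1.1, Table 3-1) |
| Set called ITT | Dosed in 0117 (9.3.1.1) | Randomized in 0116, dosed or not (3.1.1) |
| Grouping | Treatment group in 0117 (9.4.2.1) | Original 0116 arm (6.1.2.8) |

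**2. Does any output in this SAP restore the protocol endpoint?** Tables 2.4.1 to 2.4.7, Figures 1.2 to 1.2.4 and Listing 2.4 all use the SAP ITT set. Censoring Arm B at first idelalisib discards the follow-up that the protocol endpoint would count. RPSFT adjusts the randomized comparison for crossover and does not report survival from first dose. The between-study tables cover PFS and ORR only. So none does.

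**3. Could the blinded-portion analysis supply it?** SAP 1 limits this plan to the open-label portion, and SAP 2 places the blinded-portion efficacy analysis elsewhere. Protocol 9.3.2.2 sets first 0117 treatment as the origin there, so protocol OS may be reported for the two confirmed-PD groups. That analysis is confined to data from the blinded portion. It cannot include Placebo+R/IDELA subjects, who start idelalisib in the open-label phase, or the longer OS follow-up planned in SAP 2.

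**4. Size of the population change.** Enrollment in 0117 was 161 (SAP 1.3). The number actually randomized in 0116 is not given, and the documents carry three planned sizes:

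- about 180 (protocol synopsis): 180 − 161 = 19; 19/180 = 10.6%
- about 200 (SAP 1.2 schema, 100 per arm, poorly legible): 200 − 161 = 39; 39/200 = 19.5%
- about 220 (protocol 9.5): 220 − 161 = 59; 59/220 = 26.8%

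As a check on these sizes, the plan's expected 0117 enrollment of about 180, after two losses of about 10%, reproduces from 220 (220 × 0.9 × 0.9 = 178.2) but not from 180 (180 × 0.9 × 0.9 = 145.8). That favours the larger planned size but does not establish the actual one. Because placebo subjects could delay idelalisib after enrolling (protocol 5.1.2), 161 is an upper bound on the number dosed in 0117.

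**5. Size of the time shift.** For an Arm B subject who takes idelalisib:

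OS from randomization = OS from first idelalisib + (first idelalisib date − randomization date).

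The bracketed lag is not given anywhere. The SAP's Arm B curve also contains subjects who never crossed over, so even the net direction of the difference from the protocol curve is unknown.

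**The case against.** The best defence is that the SAP's choice is sensible and in plain sight. Protocol 3.2.2.1 says OS here carries on the survival assessment begun in 0116. Protocol 9.3.2.3 lets open-label analyses use combined data, depending on the endpoint. The SAP states the new origin or set in 3.1.1, Table 3-1, 6.1.1 and 6.1.2.8, and labels its OS outputs with the ITT set. The randomized comparison, with censoring at crossover and RPSFT, is also the better route to an effect of idelalisib on OS. Survival from first dose conditions on surviving to that dose, and for open-label placebo subjects the start date could be the investigator's choice. Finally, the dates appear in listings (SAP 4.1 and Listing 2.4), so the estimate could be recovered.

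Most of this stands. It supports keeping the randomized OS and rules out any suggestion of concealment. But the two protocol passages give a rationale and a choice of data source. Neither rewrites the OS definition or the dosed-subject ITT set, so the departure belongs in SAP 6.2. Listings from which someone could compute an estimate are not a planned estimate.

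A reader might go further and infer that protocol OS is reported nowhere. The documents do not show that: the blinded-portion analysis is separate, and its plan is not among them.

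**Conclusion.** The point holds as a discrepancy in definition and declaration, with one real gap: nothing in this SAP estimates OS from first idelalisib. For open-label Placebo+R/IDELA subjects, and for long-term follow-up, the blinded-portion analysis cannot fill it.

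The SAP OS set exceeds 0117 enrollment by about 19 to 59 subjects (11% to 27%), assuming 0116 randomized 180 to 220. A reader might also want to say by how many months the SAP inflates Arm B survival. The documents do not support any such figure, since neither the lag to idelalisib nor survival from that point is given.

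The analyses are descriptive and no hypothesis test is affected, so the consequence is for interpretation and traceability.

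**What to change.** - Keep the randomized OS analysis, the analysis censored at crossover and the RPSFT analysis.
- Add to SAP 6.1.2.8 a descriptive Kaplan-Meier OS from first idelalisib dose for Placebo+R/IDELA and Placebo+R (PD)/IDELA in the FAS. Note beside it that it conditions on surviving to idelalisib and that the investigator could choose the start date for open-label placebo subjects. Use the first-idelalisib date that Table 3-1 already sets for these groups. For a subject who switched while still in 0116, that date precedes 0117 entry, and the text should say so.
- List the changed OS origin and the redefined ITT set in SAP 6.2.

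The cost is one table, one curve and a few lines of SAP text. The dosing and survival dates are already collected, and SAP 6.1.2.8 already uses the first idelalisib date for Arm B.

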6.1.2. Analysis Methods for Efficacy Endpoints

6.1.2.1. Progression-Free Survival

PFS will be described in the FAS using Kaplan-Meier methods by treatment groups. Median PFS with Q1 and Q3, the Kaplan-Meier estimates of PFS rate with corresponding 95% CIs will be presented at 24, 48 weeks and so forth depending on the follow-up duration. The Kaplan-Meier curve will also be plotted.

The date of definitive CLL progression will be the timepoint at which progression is first identified by relevant objective radiographic or clinical data by the IRC.

Data will be censored on the date of the last tumor assessment (including assessments with a not evaluable [NE] outcome) for subjects who do not have disease progression, or who do not die on study. Data will also be censored on the date of the last tumor assessment (including NE) prior to the initiation of new anti-tumor therapy, or prior to ≥ 2 consecutive missing tumor assessments before disease progression or death. Subjects without adequate baseline tumor response evaluation will be censored on the baseline reference date for efficacy endpoints.

For subjects with disease progression by the IRC, the reasons for PD will be summarized by treatment groups.

The following disease progression criteria will be included:

- Progression based on index lesion
 - Increase from the nadir by \geq 50% in the SPD of index lesions
 - A new node that measures > 1.5 cm in the LD and > 1.0 cm in the LPD
 - Increase from the nadir by \geq 50% in the LD of an individual node
- Progression based on non-index lesion
 - Unequivocal increase in the size of non-index disease
- Progression based on hepatomegaly
 - New or recurrent hepatomegaly
 - Hepatic progression
- Progression based on splenomegaly
 - New or recurrent splenomegaly
 - Splenic progression
- Progression based on hematological parameters confirmed by bone marrow
 - The current platelet count is $< 100 \times 10^9$ /L and there has been a decrease by >50% from the highest on-study platelet count
 - The current hemoglobin is < 110 g/L (11.0 g/dL) and there has been a decrease by > 20 g/L (2 g/dL) from the highest on-study hemoglobin
- Transformation to a more aggressive histology

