7.5.5. Non-Evaluable

In a subject who does not have evidence of PD, the occurrence of any of the following conditions indicates a response status of NE:

- There are no images or inadequate or missing images
- Images of the liver and spleen are missing at that time point (with the exception that absence of splenic images will not result in an NE designation in a subject known to have undergone splenectomy).

Note: A time-point will be considered to have a response of NE if any index lesion is missing. PD may be assigned at any time point regardless of the extent of missing index or non-index lesions. Missing non-index lesions will not impact the ability to assess for response or disease progression.

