9.3.2.4. Calculation of Tumor Control and Patient Well-Being Variables

Tumor control assessments will be based on standardized IWCLL criteria {Cheson 2012, Hallek 2008}, as specifically modified for this study considering the pharmacology of idelalisib. The individual and composite endpoints of response and progression (considering changes in lymph node area, liver and spleen size, bone marrow, platelet counts, hemoglobin, neutrophil counts, and peripheral blood lymphocyte counts) will be determined. Tumor control will be documented at each assessment by response category (eg, CR, PR, SD, definitive PD, NE, ND) as defined for each response parameter, SPD value, percentage change in SPD values from baseline or nadir, date that response is first documented and date of definitive CLL progression.

The date of definitive CLL progression will be the timepoint at which progression is first identified by relevant objective radiographic or laboratory data. Because of the characteristic redistribution lymphocytosis that is expected with PI3Kδ inhibition, lymphocyte count will be ignored in the evaluation of progression. Changes in tumor status as provided by the investigator and changes in tumor status as adjudicated by the IRC (see Section 10.4.2) will be described. The findings of the IRC will be considered primary for analyses of all tumor control endpoints.

The following censoring conventions will be applied:

- PFS and DOR: Data from surviving, non-progressing subjects will be censored at the earliest of the time of initiation of antitumor treatment other than the study treatment or the last time that lack of definitive CLL progression was objectively documented. Data from subjects who have CLL progression or die after ≥2 consecutive missing tumor assessments will be censored at the last time prior to the missing assessments that lack of definitive CLL progression was objectively documented.
- OS: Data from surviving subjects will be censored at the last time that the subject was known to be alive.

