6.1.2.2. Overall Response Rate

Responses will be categorized as CR, PR, stable disease (SD), or PD. In addition, a response category of not evaluable (NE) is provided for situations in which there is inadequate information to otherwise categorize response status. A response category of no disease (ND) is included for situations in which there is no evidence of tumor either at baseline or on study.

The ORR using the IRC assessments will be presented with 95% CI by treatment groups. In the calculation of response rates, subjects who do not have sufficient baseline or on-study tumor assessment to characterize response will be included in the denominator.

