6.1.2.3. Lymph Node Response Rate

LNR rate will be presented with 95% CI by treatment groups. Only subjects that have both baseline and ≥ 1 evaluable post-baseline SPD will be included for this analysis.

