6.1.2.5. Time to Response and Duration of Response

TTR and DOR will be evaluated using IRC assessments based on subjects who achieve a CR or PR. Descriptive statistics will be provided for TTR. DOR will be summarized using Kaplan-Meier methods (medians, Q1, Q3, and corresponding 95% CIs) and the Kaplan-Meier curves will also be provided by treatment groups.

For the DOR analysis, data will be censored with the same manner as described in Section 6.1.2.1 for subjects who do not have disease progression, or who do not die on study, or start new anti-tumor therapy, or have ≥ 2 consecutive missing tumor assessments before disease progression or death.

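### The SAP lets a not-evaluable assessment set the PFS and DOR censoring date, an undeclared departure from the protocol, which requires objective documentation of no progression

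*SAP*

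**What the plan says.** SAP section 6.1.2.1 covers subjects with neither progression nor death on study as follows: "Data will be censored on the date of the last tumor assessment (including assessments with a not evaluable [NE] outcome". It repeats the NE inclusion for the start of new antitumor therapy and for two or more consecutive missing assessments before an event. For DOR, SAP section 6.1.2.5 says that "data will be censored with the same manner as described in Section 6.1.2.1".

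Protocol section 9.3.2.4 gives one set of conventions for both endpoints. A surviving subject without progression is censored at the earlier of the start of other antitumor treatment and "the last time that lack of definitive CLL progression was objectively documented". An event after two or more consecutive missing assessments is censored at the last such documentation before the gap.

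On the meaning of NE, SAP section 6.1.2.2 says that "a response category of not evaluable (NE) is provided for situations in which there is inadequate information to otherwise categorize response status". Protocol section 7.5.5 lists as one NE condition: "There are no images or inadequate or missing images". It also notes: "A time-point will be considered to have a response of NE if any index lesion is missing".

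The SAP has one further rule with no counterpart in the protocol: "Subjects without adequate baseline tumor response evaluation will be censored on the baseline reference date for efficacy endpoints". SAP section 6.2, the place for changes from the protocol's efficacy analyses, reports only that the per-protocol and safety analysis sets are dropped. The revision table in SAP section 12 has no entries.

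**The concern.** A censoring date says how long a subject was known to be free of progression. The protocol ties it to objective evidence. The SAP lets it rest on a time point that the review committee could not evaluate, possibly one without images. Progression-free time is then credited for a period in which progression status was not established.

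PFS and DOR by independent review are main tumor-control results of the open-label phase, reported as Kaplan-Meier curves and estimates. A reader with the protocol in hand would assume its censoring rule applies, and nothing in SAP section 6.2 says otherwise.

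**Working it through.** The documents state no figure on this point, so there is none to reproduce. The check compares the texts, works out the date shifts, and then looks at direction and size.

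**1. The rules side by side**

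| Situation | Protocol 9.3.2.4 | SAP 6.1.2.1 |
|---|---|---|
| No event | Last objective documentation of no definitive progression | Last tumor assessment, NE included |
| New antitumor therapy | Earlier of therapy start and last such documentation (surviving, non-progressing subjects) | Last assessment before therapy, NE included |
| Event after two or more missing assessments | Last such documentation before the gap | Last assessment before the gap, NE included |
| Inadequate baseline | No rule | Baseline reference date |

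**2. Does an NE date meet the protocol standard?** Not when the reason is absent or inadequate images. When one index lesion is missing from an otherwise readable scan, the time point is NE but partly informative, and protocol section 7.5.5 allows progression to be called despite missing lesions.

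**3. Date shifts.** Radiology visits through week 48 fall on Days 57, 113, 169, 253 and 337.
- Last scan NE at week 24: 169 − 113 = 56 days later under the SAP.
- Last scan NE at week 36: 253 − 169 = 84 days later.
- NE at weeks 36 and 48: 337 − 169 = 168 days later.
- Adequate baseline, then only NE at weeks 8 and 16: baseline under the protocol, week 16 under the SAP (+16 weeks).

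**4. Direction of the NE element alone.** Hold the events and all other parts of the rule fixed. The Kaplan-Meier estimate is S(t) = ∏(1 − d_j/n_j) over event times t_j up to t. Admitting NE dates moves some censoring times later and none earlier, so each n_j is the same or larger with d_j unchanged. Every factor, and so S(t), is the same or larger.

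**5. The full rules have no fixed direction.** Take two subjects.
- Subject 1: stable disease at week 24, new therapy at week 30, end-of-study scan without progression at week 31. Protocol date: min(30, 31) = week 30. SAP date: week 24.
- Subject 2: progression on an unscheduled scan at week 28 (unscheduled scans count, SAP section 3.6.1).

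At week 28 the protocol curve is 1 − 1/2 = 50% and the SAP curve is 1 − 1/1 = 0%. The inadequate-baseline rule can also make the SAP date earlier and remove an event.

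**6. Size, under assumptions.** Both censoring dates were applied to the same simulated subjects, isolating the NE element.
- *Simple setting:* exponential PFS with median 6, 12 or 20 months; dropout 2% per month; cut-off at 36 months; 5%, 10% or 20% of scans NE at random; 20,000 subjects each. SAP minus protocol is about +0.1 to +0.5 points at weeks 48 and 96. For example, with median 20 months and 20% NE, week 96 is 47.4% under the protocol rule and 47.9% under the SAP rule. The scan-based median does not change in any scenario.
- *NE allowed to cluster before dropout:* medians 12, 20 and 30 months; none or 20% of the event hazard as deaths; data cut uniform over weeks 78 to 156; dropout 0.15 per year; NE in 5/10/20% of scans and 5/25/50% of last scans before dropout; progression callable at 0/50/100% of NE scans; 120,000 subjects each. SAP minus protocol is +0.1 to +1.3 points at week 96 and 0.0 to +0.7 at week 48. For DOR 80 weeks after response it is +0.2 to +1.3. Dates differ for 5% to 34% of event-free subjects, by 11 to 15 weeks on average.
- *Stress setting:* NE in 20% to 30% of scans and 50% to 100% of last scans before dropout; dropout 0.15 to 0.30 per year; median 20 months. Week 96: +1.2 to +4.2 points.

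**7. Scale.** At 46.3% PFS with 110 subjects (planned per arm of the primary study, protocol section 9.5), the binomial standard error is √(0.463 × 0.537/110) = 4.8 points.

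**The case against.** The strongest reply has four parts.

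*A separate open-label SAP was foreseen, and the analyses are descriptive.* Both are true (protocol section 9.3.2.3; SAP section 3.5.2). But protocol section 9.3.2.4 is not limited to the blinded portion. A separate SAP may set another rule, but it should declare it. The descriptive status limits the severity.

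*NE is not evidence-free.* Protocol section 7.5.5 assigns NE only where there is no evidence of progression, and section 7.3 calls for clinical tumor assessment at each clinical visit. This stands in part. Absence of evidence, possibly with no images, is still not objective documentation.

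*The protocol rule is not clearly more accurate.* This stands. Against fully evaluable scans at week 96, the SAP rule errs by 0.0 to +1.6 points and the protocol rule by −1.2 to +0.4. In the stress setting the figures are 0.0 to +3.4 and −3.9 to 0.0. The case for change therefore rests on consistency with the protocol and disclosure.

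*The SAP is not inconsistent with itself.* A reader might contrast this rule with the inadequate-baseline rule, or with SAP section 6.1.2.3, where only subjects with a baseline and at least one "evaluable post-baseline SPD will be included for this analysis". Those serve other purposes: change cannot be measured without a baseline, and lymph node response is a numeric measure. The contrast adds little.

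**Conclusion.** The conflict is real and undeclared: a no-image or inadequate-image NE date can set the SAP censoring date but does not meet the protocol's standard. The NE element taken alone can only leave the curve unchanged or raise it.

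Two stronger readings are not supported. First, a reader might infer that the SAP's PFS curve must lie on or above the protocol's. It need not, because the full rules also differ on new therapy and on inadequate baseline (step 5). Second, a reader might infer that reported PFS is materially inflated. NE rates are not in the documents. The 0.1 to 1.3 points at week 96 rest on the assumed inputs and are small beside a standard error of 4.8. Larger shifts appeared only where NE scans were assumed frequent and clustered before dropout.

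The simulations also assume regular scans. The current protocol has ended scheduled 12-weekly CT/MRI (section 7.3), and SAP Appendix 2 sends some imaging after unblinding to standard of care. The documents do not say whether a visit without imaging would be recorded as NE. With no formal comparison affected, the issue is minor.

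**What to change.** 1. In SAP section 6.1.2.1, and so in 6.1.2.5, censor the main PFS and DOR analyses at the last evaluable (non-NE) assessment documenting absence of definitive progression. If there is none, use the baseline reference date for PFS and the response date for DOR.
2. State that an NE visit counts as an assessment, not as missing, under the rule on two or more consecutive missing assessments. Neither document settles this, and stating it keeps the event set the same in both versions.
3. Keep the NE-inclusive rule as a sensitivity analysis. Report how many subjects' censoring dates differ and by how many weeks.
4. If the NE-inclusive rule stays as main, declare it in SAP section 6.2 and show the protocol rule beside it.

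The cost is a few words in section 6.1.2.1 and one sensitivity table covering PFS and DOR, plus a line in section 6.2 only under option 4. Reported follow-up becomes slightly shorter. Last-evaluable censoring can err low when NE scans in truth exclude progression, by up to 1.2 points at week 96 in the main settings and 3.9 in the stress setting. That is why both results should be shown.
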